## 9.0 MONITORING OF PATIENTS

### 9.1 Table of Required Observations

#### Arms 1 & 2 (28-Day Cycles)

	Baseline	Days 1-5 of every cycle	Weekly During Cycle 1	Weekly During All Cycles	Pre-Odd Cycles (cycles 3+)	Pre- Even Cycles	Off Treatment	30 Days post-last dose
TRC102		6						
Temozolomide		7						
Glucocorticoids Dose Evaluation	1				5		8	
AE Evaluation	1		12		5	5	8,10	11
MRI	1				5		8	
H&P/Neuro Exam	1				5	5	8	
KPS	1				5	5	8	
Vital Signs	1,2		12		2,5	2,5	2,8	
CBC, Diff, Platelets	1			9,12	5,9	5,9	8,9	
Serum Chemistry	1,3		12		3,5	3,5	3,8	
APTT or PTT	1							
Serum Pregnancy Test	1,4							
Archived Tumor Tissue	13							

- 1– All baseline measurements must be done within minus 21 calendar days of treatment administration unless otherwise specified.
- 2– Including blood pressure, respiratory rate, heart rate, temperature, weight, height: height is required at baseline only; weight is required at pre-odd cycle evaluations only.
- 3– Including albumin, alkaline phosphatase, total bilirubin, calcium, creatinine, magnesium, phosphorus, potassium, SGOT, SGPT, sodium.
- 4– For women of child-bearing potential.
- 5– Within minus 5 calendar days of cycle start.
- 6– TRC102 is administered orally on Days 1-5 of each 28-day cycle (see Section [4.3.1](#)). Patients are required to keep a medication diary.
- 7– Temozolomide is administered orally on Days 1-5 of each 28-day cycle (see Section [4.3.2](#)). Patients are required to keep a medication diary.
- 8– Evaluations done within +7 days of off treatment date unless indicated: do not repeat: if MRI within minus 14 days of off-treatment date; if H&P/neuro, KPS, labs within minus 5 days of off-treatment date.
- 9– If ANC < 1500 or plts < 100,000, CBCs/differentials will be repeated twice a week until counts are recovered (ANC  $\geq$ 1500 or plts  $\geq$ 100,000) per protocol. If counts are recovered (ANC  $\geq$ 1500 or plts  $\geq$ 100,000) on day of scheduled drawing do not repeat until next protocol schedule day
- 10 – Adverse Events must be followed for at least 30 days from last dose of TRC102.
- 11– Perform within +14 days of the 30-day post-last dose date.
- 12–  $\pm$  1 day
- 13– Unstained slides from initial resection at diagnosis of glioblastoma, if available (see Section [9.5.1](#))

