#### 4.3.2 Temozolomide Administration

Temozolomide will be administered orally once a day for 5 consecutive days and repeated every 28 days. The dose will be 150 mg/m^2/day.

The dose administered will be determined using the body surface area (BSA) calculated at the beginning of each cycle. The BSA will be calculated from the height obtained at the baseline evaluation and from the weight obtained at the most recent pre-odd-numbered cycle evaluation before each 5-day TMZ treatment. Prior to each 5-day treatment with temozolomide a complete blood count (CBC) has to be obtained (within -5 days prior to dosing). The start of all 5-day TMZ treatments will be scheduled every 4 weeks (28 days, +3 days) after the first daily dose of temozolomide of the preceding 5-day treatment.

If liver function tests (alkaline phosphatase, total bilirubin, SGOT, SGPT) are abnormal, the decision to initiate temozolomide treatment should carefully consider the benefits and risks for the individual patient. For patients with significant liver function abnormalities, the benefits and risks of continuing treatment should be carefully considered.

Blood counts will be evaluated weekly. Within -5 days prior to the first dose of each 5-day TMZ treatment, the patient must have an ANC  $\geq$  1500/uL and platelet count  $\geq$  100,000/uL. On Day 1 of each cycle (within -5 days) all **non-hematological** toxicity grades 3 or 4 (except for alopecia, nausea and vomiting), related at least possibly to TMZ must have resolved (CTCAE grade  $\leq$  1 [or tolerable grade 2]). If toxicity persists, treatment should be delayed by one week for up to 3 consecutive weeks and directions for dose reduction should be followed (see Section [5.2](#)). If after 3 weeks of delay all toxicity has still not resolved then any further adjuvant treatment with temozolomide should be stopped (patient is off treatment).

For this study of the combination treatment of temozolomide and TRC102, the dose of temozolomide will remain at 150mg/m^2 for the duration of the study and not escalate to 200 mg/m^2. If during the first cycle the patient experiences **platelets < 50,000/uL and/or**

**ANC < 1000/ $\mu$ l and/or a non-hematologic toxicity  $\geq$  grade 3 then patient should follow directions for dose reduction in Section [5.2](#).**

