## **5.0 DOSING DELAYS/DOSE MODIFICATION FOR TOXICITY**

Clinically significant adverse events or abnormal laboratory values assessed as unrelated to disease progression, intercurrent illness, or concomitant medications require dose delay and dose modification. Such toxicities must have an attribution of possible, probable, or definite to TRC102 or temozolomide (see Section [9.2.2](#)).

In general, if toxicity occurs that is attributed to only one of the agents, only that agent should be dose-reduced/modified. The dose of the other agent can be maintained at the same level. If multiple toxicities occur, dose modification decisions should be based on the most severe toxicity.

**Because the protocol is designed to look at the effects of a combination treatment of TRC102 with TMZ, if either TRC102 or TMZ is permanently discontinued, the patient will be off treatment.**

For patients experiencing toxicity meeting the criteria below, the attributed drug(s) will be stopped. If the patient recovers ( $\leq$  grade 1 [or tolerable grade 2 for non-hematologic toxicity] or  $\leq$  baseline) a dose reduction is required for subsequent doses. Skipped doses will not be made up. If there is any question or confusion concerning a toxicity, the treating site should contact the ABTC Central Office to determine patient's toxicity status. The ABTC Central Office, with the Study Chair, will make the final decision.

- Hematological toxicities will require dose modification if any of the following occur and complete blood counts and differentials were obtained according to the mandated schedule (CBC, differential, and platelets drawn twice a week until the ANC  $\geq 1500/\text{mm}^3$  and platelets  $\geq 100,000/\text{mm}^3$ ): grade 3 or 4 lymphopenia will not be considered a toxicity requiring dose modification.

- ANC of  $< 500/\text{mm}^3$ .

- Platelets < 25,000/mm^3.
- Febrile neutropenia
- Any hematological toxicity that prevents administration of > 80% of the planned TRC102 and temozolomide doses

➤ Non-hematological toxicities will require dose modification if any of the following occur:

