- Grades 3-4 severity (except nausea, vomiting, and diarrhea without sufficient prophylaxis; except alopecia; except grade 3 hyperglycemia; except grade 3 electrolyte disturbances that are asymptomatic and that respond to replacement therapy; and except grade 3 neurologic toxicity responding within two weeks to steroids, anticonvulsants, or electrolyte correction. A subject's first episode of deep venous thrombosis (DVT) or pulmonary embolism (PE) will not require dose modification.)

*ANY TOXICITY (AS DEFINED ABOVE) CAUSING DELAY IN TREATMENT OF OVER 21 DAYS IN THE START OF A CYCLE WOULD RESULT IN TAKING THE PATIENT OFF TREATMENT.*

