### 5.1 Dose Modification for TRC102

The dose levels and the general approach to TRC102 dose modification on this trial are shown below. Adverse events (AEs) should be treated with the appropriate maximum supportive care, and dose reductions should be clearly recorded on the case report form.

Dose reductions are required for any clinically significant toxicity as defined above. Dosing will stop until the toxicity has resolved to ≤ grade 1 (or tolerable grade 2 for non-hematologic toxicity) or ≤ baseline. The maximum length of time that TRC102 can be held is 21 days. If treatment-related toxicity is not resolved in ≤ 21 days, the patient will be removed from treatment. After resolution, when dose reduction is permitted, the dose of TRC102 will be modified as stipulated below, with a maximum of 2 dose reductions. If there is any question, the ABTC Central Office and the Study Chair should be contacted.

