### 5.2 Dose Modification for Temozolomide

Clinically significant toxicities having an attribution to TMZ of possible, probable or definite will result in the following TMZ dose modifications. Dosing is based on toxicity during the prior treatment cycle. If multiple toxicities are seen, the dose administered should be based on the dose reduction required for the most severe grade of any single toxicity.

Blood counts will be evaluated weekly. Within -5 days prior to first dose of each 5-day TMZ treatment the patient must have an ANC  $\geq 1500/\text{ul}$  and platelet count  $\geq 100,000/\text{ul}$ . On Day 1 of each cycle (within -5 days) all **non-hematological** toxicity grade 3 or 4 (except for alopecia, nausea and vomiting) must have resolved (CTCAE grade  $\leq 1$  [or tolerable grade 2]). If toxicity persists, treatment should be delayed by one week for up to 3 consecutive weeks. If after 3 weeks of delay all toxicity has still not resolved then any further treatment with temozolomide should be stopped (patient is off treatment).

**Dose reductions:** If any non-hematological toxicity observed during the most recent pre-cycle evaluation was CTCAE **Grade > 2** (except for alopecia, nausea and vomiting) **and/or if platelets < 50,000/ul and/or ANC < 1000/ul**, then the dose should be reduced by one dose level (see table below). For patients who would require dose reductions to a dose level  $< 100\text{mg}/\text{m}^2/\text{day}$ , temozolomide will be **stopped**. Also, if any of the same non-hematological **Grade 3 toxicity recurs** (except for alopecia, nausea and vomiting) after reduction for that toxicity, then temozolomide will be **stopped** (patient is off treatment).

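### The required chemistry panel omits glucose although hyperglycemia is a listed temozolomide toxicity, and Sections 5.0 and 5.2 differ on which grade 3 non-hematological events, hyperglycemia included, reduce the temozolomide dose

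*Combined protocol and SAP*

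**What the plan says.** **Monitoring.** Section 9.1 schedules serum chemistry at baseline, weekly in cycle 1, before every later cycle and at off treatment. Footnote 3 gives its content: "Including albumin, alkaline phosphatase, total bilirubin, calcium, creatinine, magnesium, phosphorus, potassium, SGOT, SGPT, sodium". Hyperglycemia is named in three other places: as a known temozolomide toxicity (Section 9.2.1.2), in the Section 5.0 dose rule, and in Section 10.1, item 1, among the non-tumor explanations for neurologic worsening.

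**Dose rules.** Section 5.0 covers toxicity attributed to TRC102 or temozolomide. Its preamble says that "abnormal laboratory values assessed as unrelated to disease progression, intercurrent illness, or concomitant medications require dose delay and dose modification". Its list of grade 3-4 non-hematological triggers carries several exceptions, among them "except grade 3 hyperglycemia; except grade 3 electrolyte disturbances that are asymptomatic and that respond to replacement therapy". Where a toxicity is in question, "The ABTC Central Office, with the Study Chair, will make the final decision".

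Section 5.2 then sets the temozolomide rule. The trigger begins "If any non-hematological toxicity observed during the most recent pre-cycle evaluation was CTCAE" and continues with a grade above 2; the only events excepted are alopecia, nausea and vomiting. The consequence is one dose level down. Section 4.3.2 sends first-cycle events to the same place: for a non-hematologic toxicity at or above "grade 3 then patient should follow directions for dose reduction in Section" 5.2.

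**The concern.** There are two separate gaps.

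First, the protocol treats hyperglycemia as relevant to safety, to dosing and to the reading of neurologic decline, yet never requires the measurement that would show an asymptomatic case. Evaluating toxicity is the first secondary objective. Sections 4.2, 5.0 and 5.1 also accept recovery to baseline as a recovery standard, and without a required baseline glucose that standard cannot be applied to hyperglycemia from required data.

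Second, two sections give different exception lists for the same drug. A site following one would leave temozolomide unchanged after an event for which a site following the other would reduce it. Under Section 5.2, recurrence of the same grade 3 toxicity after a reduction stops temozolomide, and stopping either drug ends protocol treatment.

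**Working it through.** No power or sample-size figure is involved. The check compares sections and adds simple dose arithmetic.

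**1. The panel.** Footnote 3 names 11 analytes. Five are electrolytes or minerals: calcium, magnesium, phosphorus, potassium and sodium. None is glucose. In both Section 5.0 and Section 10.1 hyperglycemia stands beside electrolyte disturbances; the panel covers the latter and not the former. No other section requires a glucose value.

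**2. The exception lists.**

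| Grade 3 non-hematological event | Section 5.0 | Section 5.2 (and first cycle through 4.3.2) |
|---|---|---|
| Alopecia | excepted | excepted |
| Nausea, vomiting | excepted if prophylaxis was insufficient | excepted without that condition |
| Diarrhea without sufficient prophylaxis | excepted | not listed |
| Hyperglycemia | excepted | not listed |
| Asymptomatic, correctable electrolyte disturbance | excepted | not listed |
| Neurologic toxicity responding within two weeks to steroids, anticonvulsants or electrolyte correction | excepted | not listed |
| First DVT or PE | no dose modification | not listed |

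The mismatch is therefore not specific to hyperglycemia.

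**3. Which section governs?** Section 5.1, on TRC102, points back to Section 5.0: "Dose reductions are required for any clinically significant toxicity as defined above". Section 5.2 opens with "Clinically significant toxicities having an attribution to TMZ of possible, probable or definite will result in the following TMZ dose modifications". That echoes Section 5.0's term for significant events but contains no explicit reference back.

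Section 5.2 also sets its own blood-count limits:
- ANC below 1000 against below 500 in Section 5.0: 1000/500 = 2.
- Platelets below 50,000 against below 25,000: 50,000/25,000 = 2.

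The shared term favors carrying the exceptions over. The separate list and separate limits favor reading Section 5.2 as a rule of its own. The text does not settle it.

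**4. Consequence for one grade 3 hyperglycemia at least possibly attributed to temozolomide.**
- If the Section 5.0 exception governs: no dose modification, 0%.
- If the Section 5.2 list governs: 150 to 100 mg/m²/day. (150 − 100)/150 = 33%. Per cycle, 5 × 150 = 750 mg/m² becomes 5 × 100 = 500 mg/m².

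**5. Retreatment.** An exception from dose modification does not by itself clear the patient for the next cycle. Section 4.2 requires all toxicities to have recovered to grade 1, tolerable grade 2 if non-hematologic, or baseline, and lists no exceptions. Sections 4.3.2 and 5.2 require grade 3-4 non-hematological toxicity to have resolved by Day 1, again excepting only alopecia, nausea and vomiting, with up to three weeks of delay before the patient is off treatment. Unresolved grade 3 hyperglycemia could thus delay or end treatment even if Section 5.0 governs the dose.

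**The case against.** **On the panel.** The footnote's list is introduced as inclusive, so it sets a minimum and sites may add glucose. Hyperglycemia is in neither the list of events possibly related to TRC102 nor the list of undetermined relationship; it is listed only for temozolomide, a commercial drug. Patients may be on corticosteroids and there is no control arm, so a glucose rate would say little about TRC102. AE evaluations and examinations are already scheduled, so symptomatic cases are sought. All of this stands. It limits the value of the test, but it does not supply a required value for a toxicity that the protocol itself names.

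A reader might infer that hyperglycemia will be recorded unevenly across sites. The trial is multicenter, so this is possible, but the documents do not describe local testing and cannot establish it. Nor would a required test guarantee uniform AE recording, because Section 9.2.2 leaves it to the investigator which laboratory abnormalities count as adverse events.

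**On the dose rule.** Section 5.0 is the general section, and its preamble already excludes values due to concomitant medications. If that preamble reaches Section 5.2, there is a strong case that its exceptions do too; one cannot rely on the former and ignore the latter. Questions also go to the Central Office and Study Chair. This makes carry-over a reasonable reading. But referral helps only when a site raises a question, and Section 5.2 read alone gives a site no reason to raise one.

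**Conclusion.** Both gaps hold on the text, and both are minor. Asymptomatic hyperglycemia has no required baseline or on-treatment value. The Section 5.0 and 5.2 exception lists differ for at least five kinds of event, with no statement of precedence for temozolomide.

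The dose difference is 33% for an affected patient. It assumes a grade 3 event at least possibly attributed to temozolomide and not to a concomitant drug, and a site that applies the Section 5.2 list as written.

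Frequency cannot be estimated: the documents give neither the rate of hyperglycemia nor local testing practice. The documents do not support a stronger claim, that toxicity results will be biased by a stated amount or that the response analysis is compromised. Section 11.0 analyzes secondary outcomes descriptively, and the primary endpoint and two-stage design are little affected. This is a point to consider for cleaner safety data and consistent dosing.

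**What to change.** 1. Add glucose to footnote 3 of Section 9.1, run on the chemistry samples already drawn.
2. State in Section 5.2 that all Section 5.0 non-hematological exceptions, and its exclusion of values due to concomitant medications, apply to temozolomide reductions. Importing hyperglycemia alone would suggest that the other exceptions do not carry over. Settle at the same time whether the nausea and vomiting exception depends on prophylaxis, since the two lists differ there.
3. State that the Section 5.2 ANC and platelet limits govern temozolomide.
4. Use the same exception list in the Day 1 retreatment rules of Sections 4.2, 4.3.2 and 5.2. Amending Section 5.2's reduction rule settles the first-cycle reductions that Section 4.3.2 refers to it, but not Section 4.3.2's own retreatment list.

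**Cost.** One word in a footnote, a few sentences in the dosing sections, and a glucose entry wherever chemistry is recorded; the case report form is not in the documents, so that last item is an assumption. No extra visit or blood draw is needed. The downside is some additional laboratory AE entry and attribution work, often steroid-related. The concomitant-medication exclusion, once stated in Section 5.2, limits any dose changes that follow.

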#### **4.2 Treatment Requirements**

All eligible patients who consent to this study must have a baseline (post-operative, if surgery is applicable) pre-treatment MRI. This baseline scan must be done within 21 days prior to the initiation of treatment.

Prior to every cycle patients must have:

- 1) ANC  $\geq$  1500/ $\mu$ l and platelets  $\geq$  100,000 / $\mu$ l.  

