**Temozolomide Dose Reduction Table**

Dose Level	TMZ Dose $\text{mg}/\text{m}^2$
starting dose	150
first dose reduction	100
second dose reduction	off treatment

- If any non-hematological toxicity observed was CTCAE **Grade 4** (except for alopecia, nausea and vomiting) then adjuvant temozolomide treatment should be **stopped** (patient is off treatment).

**Subsequent 5-day TMZ treatments:** Any dose reductions of temozolomide will be determined according to (1) non-hematological toxicity during the preceding treatment cycle, as well as (2) the worst ANC and platelets toxicity. No dose escalation should be attempted. The same dose reductions as for the second 5-day TMZ treatment should be applied.

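### Footnote 9 of the required-observations table lets twice-weekly blood counts stop when either ANC or platelets recover, while section 5.0 requires both

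*Combined protocol and SAP*

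**What the plan says.** Footnote 9 applies to the CBC row of the table in section 9.1. Its first sentence reads: "If ANC < 1500 or plts < 100,000, CBCs/differentials will be repeated twice a week until counts are recovered (ANC". The parenthesis goes on to define recovery as ANC at or above 1500 *or* platelets at or above 100,000, followed by a reference to the protocol. The second sentence repeats that *or* definition, without the reference, and adds an instruction for when it is met: "on day of scheduled drawing do not repeat until next protocol schedule day".

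Section 5.0 describes the same monitoring when it sets out which hematological toxicities call for dose modification. It applies where "complete blood counts and differentials were obtained according to the mandated schedule (CBC, differential, and platelets drawn twice a week until the ANC" is at least 1500 *and* platelets are at least 100,000.

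Other sections bear on the consequences:

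- Section 4.2 opens its retreatment criteria with "Prior to every cycle patients must have" and lists both counts at the same two thresholds. Sections 4.3.2 and 5.2 also require both.
- Sections 4.3.2 and 5.2 keep a background schedule: "Blood counts will be evaluated weekly".
- Section 5.0 includes "Platelets < 25,000/mm" (per cubic mm) among its dose-modification thresholds.
- Section 5.2 reduces temozolomide at "platelets < 50,000/ul and/or ANC < 1000/ul", and for later courses uses "the worst ANC and platelets toxicity".

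**The concern.** A rule that starts when either count is low should stop only when neither is. Footnote 9 uses *or* for both the start and the stop. When exactly one count is low, the rule is switched on and already satisfied at the same draw, and it tells the site not to redraw until the next scheduled day. Section 5.0 tells the same site to keep drawing twice a week.

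What is at stake is monitoring between cycle starts. Fewer draws during an isolated neutropenia or thrombocytopenia make it easier to miss the lowest value. That value feeds the temozolomide reduction rule in section 5.2 and the toxicity data for a secondary objective. Section 5.0 also makes its hematological dose-modification rule conditional on counts having been drawn on the mandated schedule, so a site that followed footnote 9 would not meet that condition as worded. This is a multicenter study, and different sites could follow different sections.

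**Working it through.** No sample size, power or error rate is involved. The check is a truth table on the two counts, followed by simple counting.

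**Inputs.** *Low* means ANC < 1500 or platelets < 100,000, as the case may be.

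- Trigger (footnote 9): ANC low OR platelets low.
- Stop (footnote 9): ANC not low OR platelets not low.
- Stop (section 5.0): ANC not low AND platelets not low.

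**Truth table.**

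| State | Trigger met | Footnote 9 stop met | Section 5.0 stop met |
|---|---|---|---|
| Neither low | no | yes | yes |
| ANC low only | yes | yes | no |
| Platelets low only | yes | yes | no |
| Both low | yes | no | no |

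Three states meet the trigger. In 2 of 3 the footnote's stop is already met; under section 5.0 it is met in 0 of 3. A patient with both counts low enters one of the two conflicting states as soon as one count recovers before the other. The opposite of (ANC low OR platelets low) is (ANC not low AND platelets not low), so only the *and* form is consistent with the trigger.

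**Examples at a single draw.**

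| ANC | Platelets | Footnote 9 | Section 5.0 | Dose threshold met |
|---|---|---|---|---|
| 1,600 | 40,000 | recovered | not recovered | section 5.2, platelets < 50,000 |
| 1,600 | 24,000 | recovered | not recovered | section 5.0, platelets < 25,000 |
| 450 | 120,000 | recovered | not recovered | section 5.0, ANC < 500 |

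**Draw frequency while one count stays low** (weeks × draws per week, not counting the pre-cycle CBC):

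- 7 days: 1 × 1 = 1 against 1 × 2 = 2
- 14 days: 2 × 1 = 2 against 2 × 2 = 4
- 21 days: 3 × 1 = 3 against 3 × 2 = 6

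The 21-day line uses the section 5.0 limit on delay to the start of a cycle and is an illustration, not an estimate of how long a cytopenia lasts. The nominal weekly gap is 7 days. With the ±1 day window in footnote 12 it can reach 7 + 1 + 1 = 9 days. The protocol sets no spacing for twice-weekly draws, so there is no matching maximum for that schedule.

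**After the correction.** With *and* in both recovery parentheses, the stop is the exact complement of the trigger, and all four states agree within the footnote and with section 5.0.

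**The case against.** The strongest reply is that nobody would read the footnote this way. The second *or* can be taken to mirror the first, so that whichever count was low must recover. The first sentence refers back to the protocol, section 5.0 states the full rule, and sites are told to contact the Central Office if a toxicity question is unclear. Treatment safeguards also do not depend on the footnote: both counts are needed to start any cycle, weekly counts continue, and the section 5.2 temozolomide reduction does not depend on twice-weekly draws. In the three examples the dose threshold is already recorded at the draw shown, so no reduction is lost there. Toxicity is graded by CTCAE 4.0 however often blood is drawn.

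Much of this stands, and it limits the harm:

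- Losing a reduction would need a mid-week value that crosses a further threshold and rises back before the next weekly draw. An example is platelets between 50,000 and 100,000 at one weekly draw that dip below 50,000 and return. The documents give no way to say how often that happens.
- Draw frequency changes which values are seen, not how they are graded.
- The worst-count wording appears only in section 5.2.

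The textual conflict remains. The back-reference is only in the first sentence; the second repeats the *or* without it and gives a direct instruction not to redraw. The footnote does not say that the count that was low is the one that must recover. Section 12.0 sends sites to section 9.1 for evaluation time points, so the table is a natural place to look.

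**Conclusion.** The concern holds, at minor severity. Footnote 9 contradicts its own trigger and section 5.0 in two of the three count states that start it. Followed literally, it halves scheduled draws from two a week to one while a single-lineage cytopenia lasts.

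This rests on reading *or* as printed; it appears in plain words in both recovery parentheses. The intended rule is clear from section 5.0, so this is a drafting slip, not a design choice. The effect is confined to monitoring between cycle starts, capture of the lowest counts, and how comparable the recorded worst counts are across sites. Retreatment criteria, the primary response endpoint and the two-stage rules are unaffected. Without a rate of single-lineage cytopenia in the documents, the number of patients affected is unknown.

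**What to change.** In footnote 9 of the section 9.1 table, replace *or* with *and* inside both recovery parentheses, so that each requires ANC ≥ 1500 and platelets ≥ 100,000, as in section 5.0. Keep the *or* in the opening trigger, which is correct. The cost is one word in two places. No blood draws are added beyond those section 5.0 already mandates.
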